6.1.2. Progression-Free Survival by Clinical Judgment

PFS by clinical judgment is defined as the time from start date to first document of objective tumor progression, or first time tumor progression diagnosed by investigator based on clinical judgment, or death due to any cause, whichever occurs first. PFS by clinical judgment (in months) will be calculated as (first event date – start date +1)/30.44.

PFS by clinical judgment data will be censored on the date of the last tumor assessment on study for subjects who do not have tumor progression (objective or based on clinical judgment) and who do not die while on study. Patients with documentation of a PFS by clinical judgment event after an unacceptably long interval (>17 weeks) since the previous disease assessment (objective or based on clinical judgment) will be censored at the date of the previous assessment. Patients with no on-study disease assessments (objective or based on clinical judgment) are censored at the start date unless death occurred within 17 weeks post first dose (in which case the death is an event). Additionally, subjects who start a new anti-cancer therapy prior to Progressive Disease (PD) will be censored at the date of the last tumor assessment prior to the start of the new therapy.

6.1.3. Overall Survival Time

Overall Survival (OS) is defined as the time from start date to documentation of death due to any cause. OS (in months) is calculated as (date of death – start date +1)/30.44.

Subjects who withdraw from study will have their OS time censored on the date of withdrawal, and subjects who remain alive after study completion will have their OS time censored on the last date known to be alive.

6.1.4. 5-Year Survival Rate:

5-year survival rate is defined as the percentage of patients who stay alive till after 5 years from start date.

5-year survival rate will use the same censoring rule as OS.

6.2. Safety Endpoints

Primary safety outcomes include the frequency of adverse events and serious adverse events. Adverse events of particular interest are as follows:

- *Infections and infestations.*
- *Cardiac and vascular.*
- *Skin and subcutaneous tissue:*
 - *The most common skin and subcutaneous tissue related adverse events of interest are rash (includes erythematous, macular, or scaly rash), hand foot syndrome (HFS) or palmo plantar erythrodysesthesia (PPE), dry skin and skin discoloration.*

- *Gastrointestinal.*
- *Psychiatric and nervous system.*
- *Musculoskeletal.*
- *Thyroid function.*
- *General disorders.*
- *Others.*
- *Laboratory abnormalities:*
 - *Haematologic: hemoglobin, platelet count, white blood cell count, neutrophile granulocyte count.*
 - *Non Haematologic: total bilirubin, ALT (Alanine Transaminase), AST (Aspartate Transaminase), alkaline phosphatase, GGT (Gamma-Glutamyl Transferase), total protein, albumin, BUN (Blood Urea Nitrogen), creatinine, uric acid, glucose, hypocalcemia, hyponatremia, hypophosphatemia, hypokalemia.*

6.3. Other Endpoints

Not applicable.

6.4. Covariates

None.

7. HANDLING OF MISSING VALUES

Missing data will not be imputed. Subjects with missing value for a given efficacy variable will not contribute to the analysis of that variable.

8. STATISTICAL METHODOLOGY AND STATISTICAL ANALYSES

8.1. Statistical Methods

This section gives a general overview of the statistical methodology for the efficacy and safety endpoints.

The results of this study will be presented using descriptive statistics.

All analyses will be performed on (a) all FAS subjects who receive at least one dose of Sunitinib, (b) FAS subjects who have not taken sunitinib within the past 6 months (26 weeks) and will accept sunitinib therapy, and (c) FAS subjects who have already taken sunitinib within the past 6 months (26 weeks) and will continue sunitinib therapy.

All analyses will be based on the data collected during the study.

8.1.1. Analyses for Continuous Data

Descriptive summary statistics for continuous variables will include the following: sample size, mean, median, standard deviation, minimum and maximum.

8.1.2. Analyses for Time-To-Event Data

For time-to-event endpoints, the Kaplan-Meier method will be used to obtain the estimates of median event-free time. Confidence intervals for the 25th, 50th and 75th percentiles of the event-free time will be reported based on the sign test (Brookmeyer and Crowley 1982, produced with “PROC LIFETEST” in SAS). Some time-to-event endpoints will be displayed graphically when appropriate.

8.1.3. Analyses for Categorical and Binary Data

Descriptive statistics for categorical and binary variables will be given as counts and percentages. For proportions with a 95% confidence interval (CI) specified, the CI will be 2-sided with an alpha level of 0.05 using the exact method (Clopper-Pearson interval).

8.2. Statistical Analyses

8.2.1. Analysis of Primary Safety Endpoints

Safety endpoints will be summarized for the safety analysis set.

Safety data, such as AEs, vital signs, ECOG status, laboratory data, physical examination etc., will be tabulated and listed according to Pfizer’s standard reporting algorithms. Medical Dictionary for Regulatory Activities (MedDRA) and WHO drug dictionary will be used. The severity of all AEs will be coded using NCI CTCAE Version 4.0.

For the adverse events of particular interest, 95% CI will be presented using the exact method (Clopper-Pearson interval).

8.2.2. Analysis of Secondary Efficacy Endpoints

Secondary efficacy endpoints will be summarized for the FAS.

For secondary efficacy time-to-event endpoints (PFS, PFS by clinical judgment and OS), the Kaplan-Meier method will be used to obtain the estimates of median event-free time. Confidence intervals for the 25th, 50th and 75th percentiles of the event-free time will be reported based on the sign test (Brookmeyer and Crowley 1982, produced with “PROC LIFETEST” in SAS). Some time-to-event endpoints will be displayed graphically when appropriate. Sensitivity analyses will be conducted for efficacy endpoints by excluding patients with major protocol deviations.

For 5-year survival rate, the estimate and 95% confidence interval will be calculated from the Greenwood method (produced with “PROC LIFETEST” in SAS).

9. APPENDICES

Appendix 1. DATA DERIVATION DETAILS

Appendix 1.1. Derivation of PFS by Clinical Judgment

The following is the IOTA CRF page:

INVESTIGATOR OVERALL OBJECTIVE TUMOR ASSESSMENT - RECIST (VERSION 1.1)			IOTA003
 (1) NOT DONE			
Date of Tumor Assessment (dd-MMM-yyyy):  -  - 			
Tumor Assessment			
Target Lesions (check (X) ONE only):			
 (0) No Target Lesion At Baseline			
 (1) Complete Response		 (2) Partial Response	
 (4) Progressive Disease		 (5) Not Assessed	
 (3) Stable Disease		 (6) Indeterminate	
Non Target Lesions (check (X) ONE only):			
 (0) No Non-Target Lesion At Baseline			
 (1) Complete Response		 (3) Progressive Disease	
 (5) Indeterminate		 (6) No Complete Response/No Progressive Disease	
New Lesion:			
 (1) Yes			
 (2) No			
Overall (check (X) ONE only):			
 (1) Complete Response		 (2) Partial Response	
 (4) Progressive Disease		 (5) Not Assessed	
 (3) Stable Disease		 (6) Indeterminate	

VARIABLE INFORMATION:

OPTIONAL INFORMATION:

DESIGN GUIDELINE: This page should not be used for RECIST 1.0 assessments.

This DCM should be deployed at post-baseline/screening assessments.

Place the IOTA page in a CPE separate from the general cycle information. If the tumor assessment schedule is based on weeks from randomization, use weeks in the CPE label. If the tumor assessment schedule is based on cycles, cycle may be used in the label, but it should be placed in its own CPE.

On the IOTA page, if “Not Assessed” is checked for both Target Lesions and Non Target Lesions, no option is checked for New Lesion, and “Progressive Disease” is checked for Overall, then tumor progression diagnosed by investigator based on clinical judgment is reached on the Date of Tumor Assessment.

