8.6. Data Management

Datalabs is the Electronic Data Collection (EDC) system for the study. Discrepancy management is used to identify and manage potential problems with study data. Datalabs generates discrepancies during data entry and discrepancy management whenever there is a missing or inconsistency between the data entered and the validation specifications. Datalabs identifies a problem and creates a discrepancy entry in the database.

The investigator is responsible to collect study data, including the eCRF data, laboratory data, via the EDC system in a timely manner and to ensure the integrity, accuracy, and completeness of the data.

The investigator should keep accurate records of: identity of all subjects (sufficient information to link the patients to the corresponding study data), serious adverse event forms, all related source documentation, details of treatment disposition, as well as relevant correspondence details (eg, letters, emails, meeting minutes, telephone call reports). The investigator record retention period should comply with the local regulations, or as specified in the Clinical Study Agreement, whichever is longer.

If the investigator becomes unable for any reason to continue to retain study records for the required period (eg, retirement, relocation), Pfizer should be notified. The study records must be transferred to a designee acceptable to Pfizer, such as another investigator, another institution, or to an independent third party arranged by Pfizer. The investigator must obtain Pfizer's written permission before disposing of any records, even if retention requirements have been met.

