6.1.1. Progression-Free Survival

Investigator assessed PFS according to RECIST 1.1. PFS is defined as the time from start date to first document of objective tumor progression or death due to any cause, whichever occurs first. PFS (in months) will be calculated as (first event date — start date +1)/30.44.

PFS data will be censored on the date of the last objective tumor assessment on study for subjects who do not have objective tumor progression and who do not die while on study. Patients with documentation of a PFS event after an unacceptably long interval (>17 weeks) since the previous objective disease assessment will be censored at the date of the previous assessment. Patients with no on-study objective disease assessments are censored at the start date unless death occurred within 17 weeks post first dose (in which case the death is an event). Patients with inadequate baseline disease assessment are censored at the start date. Adequate baseline is defined using the following criteria:

- Subjects with target lesions: All target lesions had measurement(s) within the baseline window (200 days) and measurable.
- Subjects with non-target lesions only: All non-target lesions had non missing assessments(s) and at least one of the non-target lesions assessed as non-indeterminate within the baseline window (200 days).

Additionally, subjects who start a new anti-cancer therapy prior to Progressive Disease (PD) will be censored at the date of the last tumor assessment prior to the start of the new therapy.

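### SAP Appendix 1.1 cannot identify clinical-judgment progression in a patient with only one lesion type when the form's code 0 box is used

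*SAP*

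**What the plan says.** SAP Appendix 1.1 reproduces the investigator tumor assessment page and derives clinical-judgment progression from it. The event is set on the assessment date when Not Assessed "is checked for both Target Lesions and Non Target Lesions, no option is checked for New Lesion", and Overall is PD. No other derivation of this event appears in either document.

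On the same page the Target and Non Target blocks each allow one tick only. The first option in the Target block is "0) No Target Lesion At Baseline" and in the Non Target block "0) No Non-Target Lesion At Baseline".

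The endpoint definition has no restriction by lesion type. SAP 6.1.2 counts as an event the "first time tumor progression diagnosed by investigator based on clinical judgment", alongside objective progression and death. Protocol 8.1.1 and 8.7 define it the same way.

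Patients with one lesion type are in scope. The adequate-baseline criteria in SAP 6.1.1 have a separate line for "Subjects with non-target lesions only", and inclusion criterion 4 (Protocol 8.2.5) does not require both lesion types.

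The companion endpoint, RECIST PFS, is tied to objective progression: "Investigator assessed PFS according to RECIST 1.1. PFS is defined as the time from start date to first document of objective tumor progression" (SAP 6.1.1).

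**The concern.** The rule is narrower than the endpoint it implements. Code 0 and Not Assessed exclude each other within a block, so a patient who correctly carries code 0 in one block can never have Not Assessed in both. For that patient the clinical-judgment event cannot be recognised, whatever the investigator concluded.

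Clinical-judgment events are all that separates the event definition of this endpoint from that of RECIST PFS. The SAP also does not say how an Overall PD record that fails the rule should be classified, so two programmers could handle it differently and both claim to follow the plan.

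**Working it through.** No sample size, power or error-rate figure is involved. The check lists the possible entries on the form and applies the rule to each.

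**Inputs.** From the form in Appendix 1.1: one tick per lesion block, and a code 0 in each block. From the rule: Not Assessed in both blocks, New Lesion blank, Overall PD. Assumption: the Non Target block has a Not Assessed box. The rule presupposes one, but the extracted page shows only codes 0, 1, 3, 5 and 6 there. Text may have been lost in extraction, so this is not treated as an error in the plan.

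**Step 1: patterns with Overall PD, New Lesion blank and no lesion assessed.** Each block is either Not Assessed or code 0, and code 0 in both is excluded: 2 × 2 − 1 = 3.

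| Target | Non Target | Patient | Current rule | Amended rule |
|---|---|---|---|---|
| Not Assessed | Not Assessed | both lesion types | found | found |
| Not Assessed | code 0 | target lesions only | not found | found |
| code 0 | Not Assessed | non-target lesions only | not found | found |

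The current rule finds 1 of 3 patterns, and 0 of the 2 that belong to patients with one lesion type. Accepting code 0 in one block gives 3 of 3.

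**Step 2: the same count without the assumed box.** Only Not Assessed with Non Target code 0 can then be entered: 1 pattern. The current rule finds 0 of 1 and the amended rule 1 of 1. The target-only gap therefore exists on the page exactly as printed. The non-target-only gap depends on the assumed box.

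**Step 3: overlap with objective progression.** Lesion-level progression can be entered in three places: Target PD, Non Target PD, or New Lesion Yes. The amended rule excludes all three, so 0 of its 3 patterns overlap with objective progression.

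**Step 4: what happens to a code 0 record.** There are two possible readings.

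- *Overall PD without a lesion finding is not taken as objective.* The visit is then no event in PFS by clinical judgment. A later progression or death may still count, but SAP 6.1.2 limits this. An event "after an unacceptably long interval (>17 weeks) since the previous disease assessment (objective or based on clinical judgment) will be censored" at that previous assessment. The limit is 17 × 7 = 119 days, or 119 / 30.44 = 3.9 months. New anti-cancer therapy before progression also leads to censoring, at the last tumor assessment before that therapy. A patient with no on-study disease assessment is censored at the start date, unless death occurs within 17 weeks of first dose. The event is thus delayed or lost.
- *Overall PD is taken as objective.* The event keeps its date in PFS by clinical judgment, but a progression with no lesion assessed also enters RECIST PFS, against SAP 6.1.1.

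In neither reading is the record identified as clinical-judgment progression.

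**The case against.** The strongest reply is that the pattern in the rule is a data-entry convention. Nothing printed on the form tells a site to leave New Lesion blank for a clinical progression, so completion instructions probably exist, and they could tell sites to tick Not Assessed for an absent lesion type as well. The rule would then work. This stands as a condition on the harm. It does not remove the point: no such instruction is in the documents, and it would contradict the printed code 0 label.

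A second reply is that the rule says what happens if the pattern occurs, not only if it occurs, and that the form is titled as an objective RECIST assessment. A code 0 record might then simply be objective progression. That also stands in part. A reader might infer that events are certainly lost and PFS by clinical judgment overstated. The documents do not support this, because under the second reading in the working nothing is lost from that endpoint and the fault is misclassification into RECIST PFS.

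Third, without the assumed Non Target box even a patient with both lesion types could not meet the rule, and code 0 would not be the distinguishing fault. That is correct, and it is why the count of 1 in 3 is stated with its assumption. A reader might go further and call the absent box a defect of the form. The extracted page cannot support that.

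Finally, an affected patient needs one lesion type, a clinical progression without lesion assessment, a blank New Lesion field and code 0 at that visit. The documents give none of these frequencies. Patterns are not patients, so neither a patient count nor a shift in the median can be inferred.

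**Conclusion.** The point holds as a gap between rule and endpoint. As written, Appendix 1.1 cannot recognise clinical-judgment progression in a patient with one lesion type who is coded as the form's labels direct, while SAP 6.1.2 counts it for everyone. The consequence is conditional on sites using code 0 at that visit. It is then one of two: a missed or delayed event in PFS by clinical judgment, or an unsupported objective event in RECIST PFS.

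On the form, 2 of the 3 relevant patterns are missed, assuming the Non Target Not Assessed box exists. The number of patients is unknown and may be small. Only secondary, descriptive efficacy endpoints are affected; the primary safety endpoint is not. The amendment should be made because the rule is explicit, the mismatch is clear and the correction costs little. It is not a threat to the study's main purpose.

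**What to change.** Amend SAP Appendix 1.1 so that clinical-judgment progression is reached on the assessment date when all of these hold:

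- Overall is Progressive Disease;
- New Lesion is blank, as now;
- each lesion block is either Not Assessed or its own code 0 for no such lesion at baseline;
- at least one block is Not Assessed.

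Add that records meeting this rule are not objective progression for RECIST PFS.

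The cost is a short SAP amendment and a small programming change. It uses fields already on the form, so no new data are collected.

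Other records with Overall PD but no lesion-level progression, such as those with New Lesion ticked No, could be queried before database closure. Protocol 8.6 already provides the route: "Datalabs generates discrepancies during data entry and discrepancy management whenever there is a missing or inconsistency between the data entered and the validation specifications". This is optional and not part of the fix.
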